4.5. SCHEDULE OF EVENTS

Schedule of events can be found in Tables 1 of the protocol (arm A), 2 (arm B) and 3 (arm C) of the Section 1 of the study protocol.

4.6. CHANGES TO ANALYSIS FROM PROTOCOL

No changes are done in statistical analysis from those planned in the final study protocol.

In this document more details about the multivariate statistical analyses have been added: for Cox's Proportional Hazards regression model on Overall Survival, total Progression Free Survival and Duration of Response the list of potential predictors have been detailed (see paragraph [9.1](#)).

5. PLANNED ANALYSES

Only the Final Analysis will be performed for this study.

5.1. DATA MONITORING COMMITTEE (DMC)

In accordance with ICH E9 [1], Data Monitoring Committee is described in the protocol.

At least 1 database lock is planned for this study (final analysis), nonetheless, any additional DMC meetings can be conducted to assess safety and efficacy of the interventions during the clinical trial. All the necessary information will be further described in the relevant documents.

In any case, none of statistical tests will be applied to the data for DMC purposes.

5.2. INTERIM ANALYSIS

There will be no Interim Analysis for this study.

5.3. FINAL ANALYSIS

All final planned analyses identified in this SAP will be performed by SPARC Consulting, Milan on behalf of CRT after Sponsor Authorization of this Statistical Analysis Plan, Database Lock and Sponsor Authorization of Analysis Sets.

All summaries and listings will be performed using the SAS System version 9.4 or later under Windows 10 PRO operating system.

Continuous variables will be summarized by descriptive statistics (number of cases, mean, standard deviation, median, minimum, maximum, first and third quartile). Categorical variables will be summarized using counts of patients and percentages 95% confidence interval will be employed, unless otherwise specified.

6. MAJOR PROTOCOL DEVIATIONS

Major protocol deviations are protocol deviations that might significantly affect the completeness, accuracy, and/or reliability of the study data or that might significantly affect a subject's rights, safety, or well-being.

Major protocol deviations include:

- Any violations of Inclusion and/or Exclusion criteria;
- Incorrect dose of investigational product taken (Dose reduced/Dose delayed/Dose delayed and reduced) for more than 3 consecutive IMP cycles;
- Repeated or severe non-compliance to intake of investigational product (less than 80% or more than 120% of the prescribed dose of LGX818 and MEK162);
- Treatment with any other investigational agent at any time during the study;
- Randomized patient who received an incorrect treatment

The above major protocol deviations will be identified and confirmed prior to or at the Data Review Meeting at the latest and they will lead to the exclusion of a subject from the PP set.

Additional major protocol violations will be identified and documented following a data review meeting prior to database lock.

7. DEFINITION OF ANALYSIS SETS AND SUBGROUPS

Agreement and authorization of patients included/excluded from each analysis set will be performed on a case-by-case basis before the database lock.

The following analysis sets have been defined for this study:

Enrolled Analysis Set [ENR]

The all patients enrolled (ENR) set contains all patients who provided informed consent for this study.

Intent-to-Treat set [ITT]

The Intent-to-Treat (ITT) set will contain all randomized patients. Subjects in the ITT population will be analysed in the treatment group to which they were assigned by the randomization schedule, regardless of which study drug they receive.

The analysis of primary and secondary variables will be carried out in the ITT set.

Safety Analysis Set [SAF]

The Safety Analysis set (SAF) will contain all randomized subjects who received at least one dose of study medication. Subjects in the SAF will be analysed in the treatment group for the study drug they actually received.

The analysis of safety will be carried out in the safety population. If there is any doubt whether a subject was treated or not, they will be assumed treated for the purposes of analysis.

Per Protocol Analysis Set [PP]

The Per Protocol Analysis set (PP) will contain all randomized subjects who did not report any major protocol deviations (as detailed [Paragraph 6](#)).

The analysis on the primary variable (OS) will be repeated in the PP.

8.2. WINDOWING CONVENTIONS

All visit windows reported in the protocol will be applied to the analysis. The visit windows are described in more details for each assessment per Arm in Table 1 (Schedule of assessment) of the protocol [2]. Moreover, only values collected at scheduled study visits/time points will be presented in summary tables. However, additional exams may be scheduled as necessary to ensure the safety and well-being of subjects who experience AEs during the study. If a repeat assessment was performed, the result from the original assessment will be presented as the result at the specific visit/time point. All collected data will be included in the data listings. Additionally, unscheduled assessments will have the prefix “UNSCHEDULED” and will be sorted by the start date to its simpler recognizing.

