21.2. LABORATORY EVALUATIONS

Laboratory data will be analyzed on the SAF set.

Descriptive summaries of hematology, blood chemistry, coagulation, thyroid function, Cardiac Muscle Enzyme and endocrine panel will be provided for actual values and changes from baseline at each visit by treatment arm.

Default frequency tabulations will be also provided for urinalysis by treatment group for each visit.

Line listings of laboratory data during the study will be provided.

Presentations for continuous variables will use SI Units: conversion will be provided using the International Laboratory Normal Ranges (SI Unit Conversion Guide, M. Laposata, NEJM, 1992).

To convert from the conventional unit to the SI unit, laboratory specific derivations will be used, multiply by the conversion factor.

Table 3- Hematology: conversion factors

Component	Conventional Unit	Conversion Factor	SI Unit
Hemoglobin	g/dL	10	g/L
Hematocrit	%	0.01	Proportion of 1.0
RBC Count	X 10 ⁶ /μl	1	X 10 ¹² /L
WBC Count	X 10 ³ /μl	1	X 10 ⁹ /L
Neutrophils	X 10 ³ /μl	1	X 10 ⁹ /L
Lymphocytes	X 10 ³ /μl	1	X 10 ⁹ /L
Monocytes	X 10 ³ /μl	1	X 10 ⁹ /L
Eosinophils	X 10 ³ /μl	1	X 10 ⁹ /L
Basophils	X 10 ³ /μl	1	X 10 ⁹ /L
Platelets	X 10 ³ /μl	1	X 10 ⁹ /L

Table 4- Biochemistry: conversion factors

Component	Conventional Unit	Conversion Factor	SI Unit
Glucose	mg/dL	0.05551	mmol/L
Sodium	mEq/L	1	mmol/L
Potassium	mEq/L	1	mmol/L
Calcium	mg/dL	0.2558	mmol/L
	mEq/L	0.5	
Chloride	mg/dL	0.250	mmol/L
	mEq/L	1	
Bicarbonate	mEq/L	1	mmol/L
Magnesium	mg/dL	0.4114	mmol/L
Urea	mg/dL	0.167	mmol/L

BUN	mg/dL	0.357	mmol/L
Uric Acid	mg/dL	59.48	μmol/L
Albumin	g/dL	10	g/L
Creatinine	mg/dL	88.4	μmol/L
Creatinine Clearance	mL/min	0.01667	mL/s
Total Proteins	g/dL	0.01	g/L
Total Bilirubin	mg/dL	17.104	μmol/L
Indirect Bilirubin	mg/dL	17.104	μmol/L
Alkaline phosphatase	units/L	1	U/L
Alanine aminotransferase (ALT)	units/L	1	U/L
Aspartate aminotransferase (AST)	units/L	1	U/L
Gamma-GT	units/L	1	U/L
HDL Cholesterol	mg/dL	0.02586	mmol/L
LDL Cholesterol	mg/dL	0.02586	mmol/L
LDH	Units/L	1	U/L
	Units/L	0.01667	μkat/L
Amylase	Units/L	1	U/L
	Units/L	0.01667	μkat/L
Lipase	Units/L	1	U/L
	Units/L	0.01667	μkat/L

Table 5- Coagulation: conversion factors

Component	Conventional Unit	Conversion Factor	SI Unit
INR	Ratio	1	ratio

aPTT	Seconds	1	seconds
PTT	Seconds	1	seconds
Protrombin time	Seconds	1	seconds
Fibrinogen	g/dL	29.41	μmol/L
	mg/dL	0.01	g/L

Table 6 – Thyroid function test: conversion factors

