21.3. CARDIOLOGICAL ASSESSMENTS

ECG and ECHO/MUGA parameters will be analysed on the SAF set.

Descriptive summaries of PR interval (ms), QT interval (ms), QRS interval (ms), QTcB interval (ms), cardiac axis (°), Ejection Fraction Value (%) will be provided for actual values and changes from baseline at each visit by treatment arm.

Default frequency tabulations will be also provided for ECG result (Normal, Abnormal) and interpretation of abnormal ECG (not clinically significant, clinically significant), type of LVEF scan (ECHO, MUGA) and ECHO/MUGA scan interpretation (Normal, Clinically insignificant abnormality, Clinically significant abnormality) by treatment arm.

Line listings of ECG and ECHO/MUGA parameters during the study will be provided.

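### The numeric peak and grade of an abnormality found at an unscheduled or repeat examination can be missing from every safety summary table and appear only in the listings

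*Supplement*

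**What the plan says.** Three rules in SAP section 8.2 matter here.

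- Summary tables: "only values collected at scheduled study visits/time points will be presented in summary tables".
- Extra examinations: "additional exams may be scheduled as necessary to ensure the safety and well-being of subjects who experience AEs during the study".
- Repeats: "If a repeat assessment was performed, the result from the original assessment will be presented as the result at the specific visit/time point".

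The section then adds that "All collected data will be included in the data listings", with unscheduled records marked as such.

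For the laboratory panels, section 21.2 plans descriptive summaries that "will be provided for actual values and changes from baseline at each visit by treatment arm". Section 21.3 does the same for the cardiac measurements: "QTcB interval (ms), cardiac axis (°), Ejection Fraction Value (%) will be provided for actual values and changes from baseline at each visit". Section 21.4 follows the same pattern for vital signs. The shells for the blood panels (Tables 58 to 75), ECG and ejection fraction (Tables 85 to 87) and vital signs (Tables 91 to 93) print n, mean (SD), median and min/max per scheduled visit.

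Section 21.1 tabulates adverse events by system organ class and preferred term, relatedness, seriousness, hospitalization, withdrawal, death and AESI (Tables 45 to 57). None of these tables is by grade.

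**The concern.** Toxicity of the study drugs, laboratory safety parameters and vital signs are stated objectives (sections 3.2 and 3.3). The plan sets aside the values taken outside the visit schedule, and by its own account those arise in patients who are having adverse events. That makes the exclusion related to toxicity. If no other table brings the values back, a reader of the tables cannot see how high a transaminase, CK or troponin rose, how far LVEF fell, or how many patients reached a given severity. The answer would have to be pieced together by hand from the line listings.

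**Working it through.** The SAP gives no figure to reproduce, so the check is textual. It asks whether any planned table restores a value that section 8.2 excludes.

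**Tracing one case.** Take an Arm A patient on Combo Target with ordinary ALT at the scheduled 4-week and 8-week visits and a marked rise on an unscheduled sample at week 6.

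1. Blood chemistry, Arm A (Table 61): the 4-week and 8-week rows use the two scheduled values. The week-6 value enters neither the mean nor the min/max.
2. Any other laboratory table: none. No shift, worst-value, out-of-range or graded table is planned for the blood panels. LLN, ULN and the clinical-significance flag are collected (Listings 23 to 25 and 28 to 30), but no summary table of these panels uses them.
3. AE tables: if the rise is reported as an AE, the patient is counted once under the preferred term (Table 46). A mild and a severe event under the same term count alike. Section 4.4 names CTCAE version 4.03 for evaluating safety, and the AE listing (Listing 54) holds the grade, but no summary table reports it.
4. Listings: the week-6 value is in Listing 24 and the grade in Listing 54.

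So the event may be visible in a table, but its size and grade are not.

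**Repeats.** If the repeat is worse than the original, the table shows the milder result. If the repeat is better, the table keeps the worse one. Section 8.2 makes no provision for an invalid original, whereas the baseline definition in section 8.1 requires a valid observation and is not restricted to scheduled or original results. The two rules should be aligned.

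**Why no loss rate can be stated.** For an excursion lasting D days, with visits T days apart, uniform onset and visits on the exact day, the chance that no scheduled visit falls inside it is 1 − D/T. The intervals T come from the shells; the durations D are assumptions.

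| Interval T | D = 7 | D = 14 | D = 21 | D = 28 |
|---|---|---|---|---|
| 14 days (nivolumab) | 0.50 | 0 | 0 | 0 |
| 21 days (nivolumab + ipilimumab) | 0.67 | 0.33 | 0 | 0 |
| 28 days (Combo Target) | 0.75 | 0.50 | 0.25 | 0 |
| 84 days (ECG and ejection fraction after week 4) | 0.92 | 0.83 | 0.75 | 0.67 |

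This shows how often the schedule misses an excursion, which is a different quantity from how often section 8.2 discards a value. For a discard, an unscheduled sample must also have been taken. If u is the chance of that, the share of excursions seen only outside the schedule is (1 − D/T) × u. The documents do not give u. Over u from 0 to 1, a 7-day excursion at 4-weekly visits gives anything from 0 × 0.75 = 0 to 1 × 0.75 = 0.75, which is too wide to quote as an estimate.

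**The case against.** The case for the plan has several sound parts.

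- A reader might infer that the tables show means only. They do not. Median and min/max are printed at every visit, so an extreme value at a scheduled visit is visible.
- A reader might infer that toxicity vanishes from every table. It does not. Section 21.1 counts all AEs reported from informed consent onwards, whatever the visit. What is missing is the numeric peak and the grade.
- A reader might infer that no table counts abnormal patients. Tables 88 to 90 give ECG and ECHO/MUGA categories by visit, and urinalysis has frequency tables. The gap is in the blood panels. The cardiac tables remain subject to section 8.2, however, and their third ECHO/MUGA category is labelled as normal yet clinically significant. The Arm C ECG shell (Table 87) also names urine parameters in its programmer note instead of QT, QTcB and ejection fraction. These shell errors need correcting.
- A reader might infer a bias between sequences because visit intervals differ by drug block. The shells keep arms and blocks separate and no comparative test is planned (section 8.3), so the documents do not support that as a finding.
- Keeping the original result stops a normal retest from hiding an abnormal first value. That is a fair reason for the rule in the by-visit tables.
- Every value is retained in the listings, and summarizing by visit on scheduled values alone is reasonable.

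The protocol is not available here, so a safety table defined only there cannot be ruled out. But section 2 says the SAP contains all details of analysis and reporting, and section 24.1 ties the tables to the shells.

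These points narrow the concern. None of them supplies a table in which an off-schedule peak or an AE grade would appear.

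**Conclusion.** The point holds in a limited form. Post-baseline unscheduled values, and repeats that differ from the original, are kept out of the laboratory, QTcB, LVEF and vital-sign summaries. No worst-value, shift or grade table brings them back, so severity can be found only in the listings. The size cannot be stated, because the rate of unscheduled sampling is unknown. The conclusion rests on the SAP and its shells being the complete set of planned outputs. It is a should-fix weakness in safety reporting and does not touch the overall survival analysis.

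**What to change.** Leave the by-visit tables on scheduled values and the original result. Amend section 8.2 so that all valid post-baseline values (scheduled, unscheduled and repeat) enter each patient's worst on-treatment value within each treatment block. Section 8.2 should define where a block starts and ends, in line with the baselines in sections 8.1 and 8.4, and say how an invalid original is handled. Then add, by arm and block:

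- for each blood panel, a shift table from the block baseline to the worst value, by CTCAE version 4.03 grade where defined and otherwise below LLN, within range or above ULN;
- summaries of maximum QTcB and minimum LVEF;
- AEs by system organ class, preferred term and maximum grade.

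The cost is some SAP wording, programming and a few extra tables. The values, reference limits and AE grades already appear in the planned listings, so no new visit or test is needed.

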8.3. STATISTICAL TESTS

No comparative tests between the three sequencing treatment arms will be performed and results will be presented as descriptive statistic.

8.4. COMMON CALCULATIONS

For quantitative measurements, change from baseline will be calculated with respect to the immediately previous baseline visit, i.e.:

- For values reported after Baseline 1 visit and before Baseline 2 visit, change from baseline will be calculated with respect to Baseline 1.
- For values reported after Baseline 2 visit (and before Baseline 3 visit, for Arm C), change from baseline will be calculated with respect to Baseline 2.
- For Arm C only, for values reported after Baseline 3, change from baseline will be calculated with respect to Baseline 3

The following formulas will be applied:

- Absolute: Value at Visit X – Baseline Value

- Relative: $((\text{Value at Visit X} - \text{Baseline Value}) / \text{Baseline Value}) * 100$

8.5. SOFTWARE VERSION

All statistical analyses will be performed using The SAS System version 9.4 or later under Windows 10 Pro operating system.

9. STATISTICAL CONSIDERATIONS

9.1. ADJUSTMENTS FOR COVARIATES AND FACTORS TO BE INCLUDED IN ANALYSES

The following adjustment for covariates is planned for this study.

The Cox's Proportional Hazards regression model on Overall Survival, Total Progression Free Survival and Duration of Response will include as covariates:

- a) Treatment sequence assigned: Arm A, Arm B, Arm C;
- b) Age (years): continuous variable;
- c) Gender: Male and Female;
- d) Melanoma Type: Cutaneous, Mucosal, Ocular;
- e) Stage at current diagnosis: IIIa, IIIb, IIIc, IV – M1a, IV – M1b, IV – M1c;
- f) Baseline LDH level: continuous variable;
- g) ECOG PS at baseline: 0, ≥ 1 ;

9.2. MULTICENTER STUDIES

This study will be conducted by multiple investigators at multiple centers (approximately 30 sites in Italy and Europe) [2]. Prior to statistical analysis, data obtained at all sites will be combined into one data set.

Due to a large number of sites in this study and a small number of patients in this site, statistical tests by site will not be performed.

9.3. MISSING DATA

Any Missing data will not be imputed (including efficacy data).

9.4. MULTIPLE COMPARISONS/ MULTIPLICITY

Not applicable for this study.

9.5. ACTIVE-CONTROL STUDIES INTENDED TO SHOW NON-INFERIORITY OR EQUIVALENCE

Not applicable for this study.

9.6. EXAMINATION OF SUBGROUPS

No subgroup analyses will be performed for this study.

10. OUTPUT PRESENTATIONS

[Appendix 1](#) shows conventions for presentation of data in outputs.

The templates provided with this SAP describe the presentations for this study and therefore the format and content of the summary tables, figures and listings to be provided by SPARC Consulting, Milan on behalf of CRT.

11. DISPOSITION AND WITHDRAWALS

All subjects who provide informed consent [ENR set] will be accounted for in this study.

The following summary tables and listings will be provided:

- A summary table of patients enrolled in the study by site per Arm (including non-randomized patients)
- A summary with the number and percentage of the screening failures and of the subjects who did not satisfy inclusion/exclusion criteria, together with a data listing containing screening failures and details of the non-satisfied criteria.
- A summary with the number and percentage of the subjects included in the analysis populations (ENR, ITT, SAF, PP) and of the reasons for exclusion from ITT, SAF and PP by treatment arm. A listing of reasons for exclusion from the analysis populations will be provided.
- A frequency table and a listing of major protocol deviations
- A frequency table and a listing of end of treatment data:
 - Completion of the trial (Yes, No)
 - Primary reason for withdrawal (Progression of disease, Death, withdrawn informed consent for the study and for FU, withdrawn informed consent for the study but NOT for FU, Subject no longer meets study criteria (after the first PD), Screening Failure, AE, Poor/Non-compliance with protocol requirements, Loss of follow-up, Administrative reason by Sponsor, Subject's decision, Other)

12. DEMOGRAPHIC AND OTHER BASELINE CHARACTERISTICS

Demographic data and other baseline characteristics will be presented for the ITT set by treatment arm.

No statistical testing will be carried out for demographic or other baseline characteristics.

The following demographic and other baseline characteristics will be reported for this study by means of default summary statistics and individual data listings:

- Demographic variables:
 - Age (years) – derived as specified in [Paragraph 12.1](#)
 - Gender at birth (Male, Female)
 - Race (White/Caucasian, Black/African American, Asian, American Indian or Alaska native, Native Hawaiian or Pacific Islander, Other)
 - Ethnic Origin (Hispanic/Latino, Not Hispanic/Latino, Mixed Ethnicity, Other)
- Vital Signs at screening:
 - Body weight (Kg)
 - Height (cm)
 - BMI (kg/m²)
 - Systolic supine blood pressure (mmHg)
 - Diastolic supine blood pressure (mmHg)
 - Heart rate (bpm)
 - Body temperature (°C)
 - Respiratory rate (breaths/min)
- ECOG PS
 - 0 = Fully active, able to carry on all pre-disease performance without restriction,
 - 1 = Restricted in physically strenuous activity but ambulatory and able to carry out work of a light or sedentary nature, e.g., light house work, office work,
 - 2 = Ambulatory and capable of all selfcare but unable to carry out any work activities. Up and about more than 50% of waking hours,
 - 3 = Capable of only limited selfcare, confined to bed or chair more than 50% of waking hours,
 - 4 = Completely disabled. Cannot carry on any selfcare. Totally confined to bed or chair,
 - 5 = Dead.

Only numbers (from 0 to 5) will be reported in tables and listings.

- Disease History of Melanoma: Initial diagnosis
 - Melanoma Type (Cutaneous, Mucosal, Ocular, Unknown)
 - If mucosal, primary site of mucosal melanoma (Head and neck, Oesophagus, Stomach, Small Intestine, Colon, Rectum, Vagina, Bladder, Other)
 - If cutaneous, primary site of cutaneous melanoma (Head, Neck, Trunk, Legs, Arms, Buttocks, Other)
 - Melanoma subtype (Superficial spreading, Lentigo maligna, Nodular, Desmoplastic, Unknown, Other)
 - Time from first diagnosis of melanoma to study enrolment (months) – derived as specified in [paragraph 12.1](#)
 - Stage at initial diagnosis (0, I, Ia, Ib, Ic, II, IIa, IIb, IIc, III, IIIa, IIIb, IIIc, IV, IVa, IVb, IVc)

- Disease History of Melanoma: Current diagnosis
 - Stage at current diagnosis (IIIa, IIIb, IIIc, IV – M1a, IV – M1b, IV – M1c)
 - Recurrence/Relapse (Yes/No)
 - If yes, time from first recurrence/relapse (months) – derived as specified in [paragraph 12.1](#)
 - If yes, time from most recent recurrence/relapse (months) – derived as specified in [paragraph 12.1](#)
- Molecular status (local) mutant (Yes, No)
If yes, type of mutation (Exon 15 V600E, Exon 15 V600K, Exon 15 V600D, Exon 15 V600R, Other)
- Childbearing potential status and pregnancy test:
 - Childbearing potential (Yes, No)
 - Post-menopausal (Yes, No)
 - Accepted to use an adequate contraception for the total study duration (Yes, No)
 - Serum pregnancy test (if applicable) done (Yes, No) and result (Positive, Negative).
- HIV test:
 - Performed (Yes, No, Not applicable)
 - Result (Negative, Positive)

